6.4.3 COVID-19 Related Risks and Risk Mitigation Measures

The following risks and risk mitigating measures apply to the time in which the study is conducted during the COVID-19 pandemic.

6.4.3.1 IMP Related Risk

Against the background of the COVID-19 pandemic, the potential risk of a subject developing COVID-19 has been considered in terms of the risk-benefit evaluation. The mode of action of the IMP – as a cyclophilin inhibitor – has been considered alongside available pre-clinical and clinical data (including class effects) and it is considered that a subject would not be at increased risk of either becoming infected with severe acute respiratory syndrome coronavirus 2 (SARS-CoV-2; the virus that causes COVID-19) or experiencing a more severe illness. That is, the IMP has no known immunomodulatory effect that would confer an increased risk to healthy subjects enrolled in the study.

6.4.3.2 General COVID-19 Related Risk Mitigation Measures

General risk mitigation against COVID-19 will be implemented in accordance with Quotient's monitoring and prevention control measures.

COVID-19 testing may be performed based on current infection rates and availability of tests. If required, it is planned that testing will comprise an antigen test performed on Day -1 prior to admission to the clinical unit and at return visits. Testing time points may be changed, and additional time points may be added throughout the study as required. The decision on COVID-19 testing and the definition of the testing time points are subject to change based on the current risk mitigation in place and will be agreed by the study team and documented in the Investigator Site File (ISF) via the Clinical Kick-Off Meeting minutes.

The risk mitigation measures, where applicable, will be amended based on emerging government guidance.

6.4.3.3 COVID-19 Vaccine-Related Risk

Approved (including health authority conditional marketing authorisation) COVID-19 vaccines eg killed, inactivated, peptide, DNA and RNA vaccines may be permitted according to the investigator's discretion and as per local guidance.

Based on the mechanism of action of the IMP, as an inhibitor of cyclophilin, there is no perceived impact on the safety of the study subjects or on the study objectives for subjects who may receive these vaccines. It is also very unlikely that administration of the IMP would interfere with COVID19 vaccination response; however, no specific preclinical or clinical investigations have been conducted at this point with rencofilstat.

6.4.4 General Risks and Overall Risk-Benefit Assessment

Collecting a blood sample from a vein may cause pain, swelling, bruising, light-headedness, fainting, and very rarely, clot formation, nerve damage and/or infection at the site of the needle stick.

During cannulation, more than one attempt may be needed to insert the cannula in a vein of a subject and it is possible that bruising and/or inflammation may be experienced at the site of cannulation.

ECG stickers on the subjects' chests and limbs may cause some local irritation and may be uncomfortable to remove but subjects will be closely monitored to ensure any local irritation does not persist.

There is no benefit to the subjects from taking part in this study. The development of a product to treat NASH and viral hepatitis-induced liver disease may be of benefit to the patients with these diseases.

The overall risk benefit balance is therefore considered to be acceptable.

7 Objectives and Endpoints

Objectives	Endpoints
Primary To determine the mass balance recovery after a single oral dose of [¹⁴ C]-rencofilstat	Mass balance recovery of total radioactivity (TR) in all excreta (urine and faeces): CumAe and Cum%Ae
To determine % parent drug unchanged versus metabolites	Parent to total radioactivity ratio for whole blood based on AUC
To perform metabolite profiling and structural identification from whole blood, urine and faecal samples ^a	Collection of whole blood, urine and faeces samples for metabolite profiling, structural identification, and quantification analysis
Secondary To determine the routes and rates of elimination of [¹⁴ C]-rencofilstat	Mass balance recovery of TR in urine and faeces separately: Ae, %Ae, CumAe and Cum%Ae by interval
To identify the chemical structure of each metabolite accounting for more than 10% of circulating TR or accounting for 10% or more of the dose in excreta	Identification of the chemical structure of each metabolite accounting for more than 10% by AUC of circulating TR or accounting for 10% or more of the dose in excreta
To evaluate the extent of distribution of TR into blood cells	Evaluation of whole blood:plasma concentration ratios for TR
To provide additional safety and tolerability information for rencofilstat	To provide additional safety and tolerability information for rencofilstat by assessing: incidence of AEs, physical examinations and change from baseline for vital signs, ECGs, and laboratory safety tests
To further explore the oral PK of rencofilstat	PK parameters for rencofilstat in whole blood and TR in plasma and whole blood following a single oral dose, including but not limited to: Tlag, Tmax, Cmax, AUC(0-last), AUC(0-inf), AUC(0-24), Lambda-z, T1/2, CL/F, Vz/F, MRT(0-last) and MRT(0-inf) as applicable

^a Metabolite profiling and identification will be reported separately from the clinical study report as a standalone document.

8 Study Design

8.1 Study Plan

This is a single centre, open-label, non-randomised, single period, single dose study in healthy male subjects designed to assess the mass balance recovery, PK, metabolite profile and metabolite identification of rencofilstat. It is planned to enrol a single cohort of 6 subjects.

All subjects will receive a single 225 mg oral dose of [¹⁴C]-rencofilstat, as a SMEDDS oral emulsion, containing NMT 6.4 MBq, in the fasted state.

Subjects will undergo preliminary screening procedures for the study at the screening visit (Day -28 to Day -2). Subjects will be admitted in the evening on the day before dosing (Day -1).

Whole blood, plasma, urine and faeces samples will be collected at regular intervals for PK analysis, TR analysis, metabolite profiling, mass balance and safety as applicable, from pre-dose to discharge from the clinical unit. Urine and faeces samples may be collected at return visits or home visits if mass balance criteria has not been met by a subject.

Subjects will be dosed on the morning of Day 1 following an overnight fast (minimum 8 h) and will remain resident in the clinical unit until up to 504 h after dosing (up to Day 22).

It is planned that subjects will be released as a group when all subjects have achieved a mass balance cumulative recovery of >90% or if <1% of the dose administered has been collected in urine and faeces within two separate, consecutive 24 h periods. This may result in the subjects being discharged as a group prior to completion of the planned residency period.

If the mass balance criteria are achieved during the planned residency period, collection of all samples (blood, urine and faeces) will be stopped once the current 24 h collection period is complete, and subjects will undergo discharge assessments.

If the mass balance criteria have not been met by all subjects on the morning of Day 22, the residency period for the subjects not achieving the mass balance criteria may be extended up to a maximum of 96 h (Day 26; 600 h post-dose). Only urine and/or faecal samples will be collected during the extended residency period.

If the mass balance criteria have not been met by all subjects on the morning of Day 26, subjects not achieving the release criteria may be required to make up to 2 return visits (each of 24 h duration) at (nominally) Day 28 (+2 days) and Day 35 (\pm 2 days) for additional collection of excreta samples (urine and/or faecal samples).

If the mass balance criteria have not been met following the return visits, then home collections of urine and/or faeces may be requested at the discretion of the investigator for individual subjects.

A subject will be considered evaluable if they have provided mass balance and PK samples for up to 21 days after drug administration or have demonstrated >90% mass balance recovery or have <1% of the administered dose eliminated in excreta for two consecutive days, whichever is sooner.

Figure 1 Study Sequence

^a If all subjects have not achieved a mass balance cumulative recovery of >90% or if a total of <1% of the dose administered has not been collected in urine and faeces within 2 separate, consecutive 24 h periods on the morning of Day 22, the residency period for the subjects not achieving the mass balance criteria may be extended up to a maximum of 96 h (Day 26). Only urine and/or faecal samples will be collected during the extended residency period.

^b If the mass balance criteria have not been met by all subjects on the morning of Day 26, subjects not achieving the release criteria may be required to make up to 2 return visits (each of 24 h duration) at (nominally) Day 28 (+2 days) and Day 35 (±2 days) for additional collection of excreta samples (urine and/or faecal samples). If the mass balance criteria have not met following the return visits, then home collections of urine and/or faecas may be requested at the discretion of the investigator for individual subjects.

8.2 Criteria for In-Study Decisions

Not applicable for this study.

8.3 Subject Withdrawal

If a subject wishes to leave the study at any time, they will be permitted to do so. Every reasonable effort will be made by Quotient to complete a final assessment/discharge procedures. Quotient will advise the sponsor of the withdrawal of any subject from the study.

Early withdrawal is defined as the date of the decision to withdraw the subject from the study. Subject completion is defined as the date of the last procedure conducted or last contact (eg unscheduled phone call or visit) for that subject.

Note that if a subject requests to leave the clinical unit earlier than the planned discharge time, eg due to unforeseen personal circumstances, they may be withdrawn from the study and may not be able to return to the clinical unit to complete the study.

This is a single dose study, therefore, after an individual subject has received a dose of IMP, withdrawal of that subject from further dosing is not possible. Subjects will be monitored for the following criteria which may require their withdrawal from some or all study procedures if continuation is not in their best interests, except when the withdrawal is a result of withdrawal of consent:

- Experiencing a serious or severe AE including but not limited to:
 - corrected QT interval by Fridericia's formula (QTcF) of >500 msec or increase in QTcF interval of >60 msec from baseline (confirmed following a repeat ECG)
 - ALT concentration >3 × the upper limit of the reference range (confirmed following a repeat ALT blood test)
- Termination of the study
- Upon the subject's request (withdrawal of consent)
- Significant deviation from the protocol
- Concurrent illness that would adversely affect subject safety or data integrity or requirement for prohibited medication
- At the discretion of the investigator

For the purpose of withdrawal criteria, baseline will be considered as the last available assessment prior to IMP dose.

For a subject who withdraws because of an IMP-related AE, every effort will be made to ensure the subject completes follow-up procedures.

Early withdrawal of consent by the subject to participate in any further activities will be distinguished from withdrawal for any of the other above reasons.

8.4 Subject Replacement

No replacement subjects are planned for this study.

8.5 Stopping Criteria

The study will be halted, and the risk to other subjects evaluated if any of the following criteria are met:

- A serious adverse reaction (ie a SAE considered at least possibly related to the IMP administration) in one subject.
- Severe non-serious adverse reactions (ie severe non-serious AE considered as, at least possibly related to the IMP administration) in two subjects in the same cohort, independent of within or not within the same system organ class.

Relatedness to IMP will be determined by the investigator.

If the study is halted, a temporary halt will be submitted to the Medicines and Healthcare products Regulatory Agency (MHRA) and ethics committee (EC) in the form of a substantial amendment. The study may be resumed or terminated; however, it will not be resumed until a further substantial amendment to resume the study is submitted and approved by MHRA and EC.

The ARSAC Practitioner will also be informed of the temporary halt.

8.6 Study Termination

After the start of protocol activities but prior to the commencement of dosing, the study may be terminated by the sponsor and investigator without consultation with the MHRA, EC, ARSAC practitioner or ARSAC. The ARSAC practitioner and ARSAC (if ARSAC research application has been submitted or approved) must be notified promptly, that the study will no longer be taking place. Notification of early termination should also be provided to the EC and MHRA within 15 days, clearly explaining the reasons for the termination.

If the study is abandoned prior to commencement of any protocol activities, the investigator or sponsor must notify the EC, MHRA, ARSAC practitioner and ARSAC (if ARSAC research application has been submitted or approved) outlining the reasons for abandonment of the trial.

New information regarding the safety of the IMP that indicates a change in the risk/benefit profile for the compound, such that the risk/benefit is no longer acceptable for subjects participating in the study may also mean termination of the study prior to dosing.

Once exposure to dosing has begun, the study will be completed as planned unless the following criteria are satisfied that require a temporary halt or early termination of the study.

- The occurrence of serious or severe AE(s), as defined in Section 8.5, if considered to be related to the IMP, as defined in Section 14.2, on the dosing day.
- Significant violation of Good Clinical Practice (GCP) that compromises the ability to achieve the primary study objectives or compromises subject safety.

If any of the above occurs, the study will be terminated if careful review of the overall risk/benefit analysis described in Section 6.4 demonstrates that the assumptions have changed and that the overall balance is no longer acceptable. In these circumstances, termination can only take place with the agreement of the investigator and sponsor. The MHRA, EC, ARSAC practitioner and ARSAC will be informed of study termination.

If it becomes necessary to consider termination of the study on the dosing day, dosing may be suspended pending discussion between the investigator, sponsor and ARSAC practitioner (where discussion is related to administration of radiation). Dosing will be stopped immediately on safety grounds.

The study may be terminated or suspended at the request of the MHRA or EC.

8.7 Lost to Follow-up

A subject will be considered lost to follow-up if they fail to return for scheduled visits and cannot be contacted by the clinical unit.

If a subject fails to return to the clinical unit for a required study visit:

- The clinical unit must attempt to contact the subject and reschedule the missed visit as soon as possible.
- Before a subject is deemed lost to follow-up, the investigator or designee must make every effort to regain contact with the participant (eg three telephone calls on three separate occasions and, if necessary, an email or letter to the participant's last known email/postal address). These contact attempts should be documented in the subject's source.
- If the subject cannot be contacted, they will be considered lost to follow-up.

8.8 Treatment Assignment

This is an open-label, non-randomised study, therefore a randomisation schedule will not be produced. Instructions to dispense and dose will be produced prior to dosing with IMP, which will dictate the order in which the treatments should be administered to each subject. The instructions to dispense and dose will be retained in the ISF.

8.8.1 Subject Numbers

Subject numbers will be allocated on the morning of dosing according to the code 001 to 006 using the lowest number available.

8.8.2 Blinding

This is an open-label, non-randomised study and therefore blinding is not required.

9 Selection of Subjects

Subjects will be recruited from the Quotient panel or by direct advertising to the public.

Before subjects are admitted to the clinical unit, The Over Volunteering Prevention System (TOPS) will be checked to ensure that each subject has not been dosed in a study within 90 days of the planned dosing date of this study.

9.1 Informed Consent

Subjects will be provided with a written explanation of the study at least the day before the screening visit. Additionally, subjects may be provided with an information video before the screening visit that introduces them to the study. In the video and/or during the screening visit, a physician or nurse will explain to each subject the nature of the study, its purpose, expected duration and the benefits and risks involved in study participation. Subjects will be informed that, for safety reasons, brief details of their involvement in the study may be revealed to other units and companies that carry out clinical studies nationally. Subjects will then be given the opportunity to ask questions and will be informed of their right to withdraw from the study without prejudice. After this explanation and before entering the study, the subject will voluntarily sign an informed consent form (ICF). Until written consent has been obtained from the subject no study specific procedure or investigation will be performed. If an amendment is made to the participant information sheet (PIS), participants will be re-consented to the most current version of the ICF(s) where appropriate.

9.2 Inclusion Criteria

- 1. Healthy males
- 2. Aged 30 to 65 years inclusive at the time of signing informed consent

- 3. Body mass index (BMI) of 18.0 to 35.0 kg/m² as measured at screening
- 4. Must be willing and able to communicate and participate in the whole study
- 5. Must have regular bowel movements (ie average stool production of ≥1 and ≤3 stools per day)
- 6. Must provide written informed consent
- 7 Must agree to adhere to the contraception requirements defined in Section 9.4

Inclusion criteria 1, 4, 5 and 7 from the list above will be re-assessed at admission or pre-dose.

9.3 Exclusion Criteria

- 1. Subjects who have received any IMP in a clinical research study within the 90 days prior to Day 1, or less than 5 elimination half-lives prior to Day 1, whichever is longer
- 2. Subjects who are, or are immediate family members of, a study site or sponsor employee
- 3. Evidence or history of current SARS-CoV-2 infection within 4 weeks prior to IMP administration
- 4. History of any drug or alcohol abuse in the past 2 years prior to screening
- Regular alcohol consumption in males >21 units per week (1 unit = ½ pint beer, or a 25 mL shot of 40% spirit, 1.5 to 2 units = 125 mL glass of wine, depending on type)
- 6. A confirmed positive alcohol breath test at screening or admission
- 7. Current smokers and those who have smoked within the last 12 months prior to screening
- 8. A confirmed breath carbon monoxide reading of greater than 10 ppm at screening or admission
- 9. Current users of e-cigarettes and nicotine replacement products and those who have used these products within the last 12 months prior to screening
- 10. Radiation exposure, including that from the present study, excluding background radiation but including diagnostic x-rays and other medical exposures, exceeding 5 mSv in the last 12 months or 10 mSv in the last 5 years. No occupationally exposed worker, as defined in the lonising Radiation Regulations 2017 [16], shall participate in the study
- 11. Subjects who do not have suitable veins for multiple venepunctures/cannulation as assessed by the investigator or delegate at screening
- 12. Clinically significant abnormal clinical chemistry, haematology or urinalysis as judged by the investigator (laboratory parameters are listed in Appendix 1). Subjects known to have Gilbert's syndrome are excluded
- 13. Confirmed positive drugs of abuse test result (drugs of abuse tests are listed in Appendix 1)
- 14. Positive hepatitis B surface antigen (HBsAg), hepatitis C virus antibody (HCV Ab) or human immunodeficiency virus (HIV) antibody results
- Evidence of renal impairment at screening, as indicated by an estimated eGFR of <60 mL/min/1.73m² using the Chronic Kidney Disease Epidemiology Collaboration (CKD-EPI; 2009) equation
- 16. History of clinically significant cardiovascular, renal, hepatic, dermatological, chronic respiratory or gastrointestinal disease, malabsorptive, neurological or psychiatric disorder, as judged by the investigator
- 17. Serious adverse reaction or serious hypersensitivity to any drug or the formulation excipients

- 18. Presence or history of clinically significant allergy requiring treatment, as judged by the investigator. Hay fever is allowed unless it is active
- 19. Donation of blood or plasma within the previous 3 months or loss of greater than 400 mL of blood
- 20. Subjects who have taken known strong or moderate CYP3A4 inducers in the 30 days before IMP administration
- 21. Subjects who are taking, or have taken, any prescribed or over-the-counter drug or herbal remedies (other than up to 4 g of paracetamol per day) in the 14 days before IMP administration (see Section 11.4). Exceptions may apply, as determined by the investigator, if each of the following criteria are met: medication with a short half-life if the washout is such that no pharmacodynamic activity is expected by the time of dosing with IMP; and if the use of medication does not jeopardize the safety of the trial subject; and if the use of medication is not considered to interfere with the objectives of the study
- 22. Subjects who have had a COVID-19 vaccine 7 days before dosing
- 23. Failure to satisfy the investigator of fitness to participate for any other reason

Exclusion criteria 3, 6, 8, 9, 13, 18, 20, 21 and 22 from the list above will be re-assessed at admission/pre-dose.

Healthy subjects who do not meet the inclusion/exclusion criteria for the study will not be enrolled.

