6.4.2 Risks Associated with Administration of Radioactivity

The dosage form will contain a radionuclide, not more than (NMT) 6.4 MBq ¹⁴C, so subjects will be exposed to ionising radiation. The effective dose that each subject will receive from 1 administration of 6.4 MBq ¹⁴C will not exceed 2.0 mSv. This is approximately 9 months of the average radiation exposure received in the UK each year (2.7 mSv; data obtained from UK Health Security Agency Ionising Radiation Exposure of the UK Population: 2010 Review [13]) and is slightly more (1.1 times) than the radiation dose that would result from 4 abdominal X-rays (0.47 mSv each). It is believed that any increase in the amount of radiation that is received above natural radiation carries a risk of later developing serious and possibly fatal conditions. The risk associated with the maximum possible dose of radiation in this study is very small indeed and is considered to be acceptable.

Extrapolation of data from epidemiological studies of cancers induced by radiation exposure indicates that the risk factor for an adult UK population of both sexes (age range 18 to 64) is 5×10^{-2} per Sv [14]. From this it can be estimated that the lifetime risk of inducing a fatal cancer in a healthy individual from the total exposure of 2.0 mSv is approximately 1 in 10,000. The lifetime risk for being diagnosed with cancer in the UK is around 1 in 2 [15], indicating that this additional risk from this amount of radiation exposure is minimal.

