15.1 Sample Size Justification

The study is exploratory and no formal sample size calculation has been made. Based on experience from previous studies of a similar design, a total of 6 subjects are to be enrolled and a minimum of 4 evaluable subjects are considered sufficient.

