9.1.2 Rules for Mass Balance Parameter Estimation

The following will be calculated for total radioactivity in urine, faeces and urine and faeces combined by Quotient Data Sciences (note that the amount excreted in pre-dose samples will not be included in the calculation of the cumulative amount excreted or in the calculation of the cumulative percentage of the radioactive dose excreted):

• The amount excreted in urine i.e. Ae(urine) and the amount excreted in faeces i.e. Ae(faeces) will be calculated for each collection interval the following formula (where matrix is either urine or faeces): using

Following Day 26, where urine/faecal collections are no longer continuous and return visits (i.e., Day 28 [±2 days] and Day 35 [±2 days]) are scheduled, additional interpolation of A_e will be calculated to estimate amount excreted on non-collection days (i.e., between Day 26 to Day 28, and Day 28 to Day 35 if required), as follows:

where Day x and Day y are the calculated amounts excreted for the preceding and proceeding days of the interval to be calculated.

Interpolation may also be calculated to estimate the amount excreted between home collects if required.

• The total amount excreted in urine and faeces combined, i.e. Ae(total), will be calculated for each collection interval using the following formula:

- The cumulative amount excreted in urine i.e. CumAe(urine) and the cumulative amount excreted in faeces i.e. CumAe(faeces) will be calculated by the incremental summation of the Ae(<matrix>) across all collection intervals (where matrix is either urine or faeces). The amount excreted in the pre-dose sample should not be included in the calculation of the cumulative amount excreted.
- The cumulative amount excreted in urine and faeces combined i.e. CumAe(total) will be calculated across all collection intervals using the following formula:

• The % amount of the total radioactive dose excreted in urine i.e. %Ae(urine) and the % amount of the total radioactive dose excreted in faeces i.e. %Ae(faeces) will be calculated for each collection interval using the following formula (where matrix is either urine or faeces):

%Ae(<matrix>) = 100 * Ae(<matrix>) / Total Radioactive Dose Administered

• The % amount of the total radioactive dose excreted in urine and faeces combined will be calculated for each collection interval using the following formula:

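### Section 9.3 does not keep out volunteers with recent earlier carbon-14 dosing, and the SAP states no action for quantifiable pre-dose radioactivity; the effect is conditional and modest, and cheap to close

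*Protocol*

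**What the plan says.** **Eligibility (Protocol 9.3).** Criterion 1 excludes volunteers who have "received any IMP in a clinical research study within the 90 days prior to Day 1". For slowly cleared drugs the required gap lengthens, through the added condition "or less than 5 elimination half-lives prior to Day 1, whichever is longer". The criterion treats a radiolabelled drug like any other IMP and does not say whether the half-life is that of the parent or of the label. Criterion 10 caps radiation exposure, this study included, at a level not "exceeding 5 mSv in the last 12 months or 10 mSv in the last 5 years", and bars occupationally exposed workers. No criterion concerns an earlier radiolabelled dose as such. The volunteer-database check in Section 9 repeats the 90 days.

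**Recruitment and dose.** Protocol Section 9: "Subjects will be recruited from the Quotient panel or by direct advertising to the public". Protocol 6.4.2 states that "1 administration of 6.4 MBq ¹⁴C will not exceed 2.0 mSv".

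**Analysis.** The primary endpoints include Cum%Ae for urine and faeces combined and the whole-blood parent:TR ratio, which SAP Table 4 bases on AUC(0-inf). On pre-dose excreta, SAP 9.1.2 says: "note that the amount excreted in pre-dose samples will not be included in the calculation of the cumulative amount excreted". Its surviving %Ae formula divides the amount excreted by the radioactive dose given in this study. SAP 10.1.2 sets pre-dose sample times to zero but is silent on a measurable pre-dose TR concentration.

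**Sampling.** Pre-dose whole blood and plasma for TR are scheduled (Protocol Appendix 2). Pre-dose urine and faeces are planned, but their absence is not a deviation (Protocol 13.1.2, 13.1.3).

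**The concern.** A drug washout and a radiation-safety cap serve other purposes. Neither ensures that label from an earlier study has left the body, and a TR assay counts every carbon-14 atom alike. Leaving the pre-dose sample out of the cumulative sum removes that sample only. It does not remove earlier label from the samples that follow.

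Two primary results are exposed. Earlier label in excreta is credited to rencofilstat recovery and could move a subject across the 90% release criterion. Earlier label in blood adds a slowly falling background to TR. That background matters most late in the profile, where it flattens the fitted terminal slope, raises TR AUC(0-inf) and lowers the parent:TR ratio. A larger TR denominator also makes the threshold of 10% of circulating radioactivity harder for a metabolite to reach.

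A subject who met every criterion would have no protocol deviation, so the deviation-based exclusions in SAP 6.2 and 6.3 would not catch the case. With six subjects, at least four evaluable and no replacements, one affected subject is 17% to 25% of the data.

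**Working it through.** **The plan's own figures.** The protocol states no sample size or power calculation ("The study is exploratory and no formal sample size calculation has been made"), and this point does not depend on one. The radiation risk in 6.4.2 reproduces: 0.0020 Sv × 0.05 per Sv = 0.0001, or 1 in 10,000.

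**1. Who is eligible.**
- Headroom under criterion 10: 5 − 2.0 = 3.0 mSv in 12 months; 10 − 2.0 = 8.0 mSv in 5 years.
- An identical earlier study uses at most 2.0 mSv, which fits.
- Criterion 1 is met at 90 days if the earlier drug's half-life is at most 90/5 = 18 days.

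**2. Excreta.** Assumptions: earlier radioactive dose equal to this one; mono-exponential clearance with half-life h days; gap g = max(90, 5h) days. Residual at Day 1 = 2^(−g/h). Amount excreted in 21 days = residual × (1 − 2^(−21/h)).

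| h (days) | g (days) | Residual, % of dose | Added to 21-day Cum%Ae | On mean of six |
|---|---|---|---|---|
| 10 | 90 | 0.195 | 0.15 | 0.02 |
| 18 | 90 | 3.125 | 1.73 | 0.29 |
| 30 | 150 | 3.125 | 1.20 | 0.20 |

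If criterion 1 is applied to the parent's half-life and the label clears more slowly, a 30-day label half-life after a 90-day gap leaves 12.5% and adds 12.5 × (1 − 2^(−0.7)) = 4.8 points (0.8 on the mean of six). At a half-life like rencofilstat's (98 h) nothing measurable remains after 90 days.

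**3. Blood.** Inputs from Protocol Table 2 at 225 mg: AUC(0-last) 53,530 and AUC(0-inf) 80,030 ng.h/mL, half-life 98.14 h, Vz/F 412.7 L. I take AUC(0-last) to end at 144 h, since sampling ran for 6 days. Applying rencofilstat's volume to an unknown earlier drug is illustrative only.
- Residual at Day 1: 0.03125 × 225 mg / 412.7 L = 17.0 ng eq/mL.
- Parent at 144 h: (80,030 − 53,530) × ln 2 / 98.14 = 187 ng/mL; at 504 h: 187 × 2^(−360/98.14) = 14.7 ng/mL.

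SAP 10.1.2 fits one log-linear slope to the observed profile. I added the residual to the 98.14 h tail at the scheduled times from 144 to 504 h and refitted that slope. The lines below first take TR equal to parent, so the uncontaminated extrapolated area is 14.7 × 98.14 / ln 2 ≈ 2,084.
- h = 18 days: residual area to 504 h = (17.0 × 18 × 24 / ln 2) × (1 − 2^(−21/18)) ≈ 5,890. TR at 504 h = 14.7 + 7.6 = 22.3 and the fitted half-life is 113 h, so the extrapolated area is about 3,640, a gain of 1,550. Total gain ≈ 7,440, or 9.3% of 80,030.
- h = 30 days: residual area to 504 h ≈ 6,800. TR at 504 h = 14.7 + 10.5 = 25.2 and the fitted half-life is 119 h, a further gain of about 2,240. Total gain ≈ 9,050, or 11.3%.

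Protocol 5.3.1 reports at least 12 metabolites, so TR probably exceeds parent. Scaling the TR baseline accordingly (parent shares of 50% and 30% are assumptions):

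| Parent share of TR AUC | TR AUC(0-inf) gain, 18 d / 30 d | Fall in parent:TR, 18 d / 30 d |
|---|---|---|
| 100% | 9.3% / 11.3% | 8.5% / 10.1% |
| 50% | 4.6% / 5.6% | 4.4% / 5.3% |
| 30% | 2.7% / 3.3% | 2.7% / 3.2% |

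At h = 10 days the fall is below 1% throughout.

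**The case against.** **The route is hypothetical.** It needs an earlier carbon-14 dose, close to the minimum gap, of a compound whose label persists for weeks. The documents give no frequency. The reference in Protocol 15.1 to previous studies of similar design does not say who ran them or that panel members repeat them. This stands, and it is why the point is conditional.

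**Detection and discretion exist.** Pre-dose blood and plasma TR are scheduled, pre-dose values are tabulated, and all concentrations are listed. SAP 6.3 lets a PK profile be excluded for a study-emergent point bearing on PK interpretation, SAP 10.1.2 lets unusual values be queried, and criterion 23 leaves the investigator discretion. This stands too: the plan can respond. It does not say in advance that it will, or how.

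**The absence of subtraction is not fully visible.** The Ae formula is missing from the available SAP text, and laboratory background handling is not described. So one can say only that no baseline correction is stated, not that none would be made.

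**A larger blood effect might be inferred.** Integrating the residual to infinity at its own half-life gives 10,618 (13%) at 18 days and 17,697 (22%) at 30 days over 80,030, and hence a parent:TR ratio 12% to 18% lower. The documents do not support that reading. The SAP extrapolates with one fitted slope, and 80,030 is the parent's AUC, which equals TR only if nothing but parent circulates.

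**Conclusion.** The gap is real. A volunteer with a similar carbon-14 dose about 90 days earlier satisfies 9.3, and the plan sets no rule for what follows if that label is still measurable. The likely size is modest. Under the stated assumptions, with a TR half-life of 18 to 30 days, one subject gains about 1.2 to 1.7 points of Cum%Ae and loses about 3% to 10% of the parent:TR ratio, depending on how much of TR is parent. The gain of 4.8 points arises only if the label outlasts a parent that itself meets the 90-day rule. It would be wrong to conclude that the recovery estimate is materially biased as planned, because nothing in the documents shows that any subject will have had earlier carbon-14. This is a worthwhile, inexpensive improvement and does not threaten the study's validity.

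**What to change.** 1. Add to Protocol 9.3 an exclusion for receipt of any carbon-14-labelled compound in the 12 months before Day 1. Criterion 10 already requires a radiation history over that period. An equal dose 365 days earlier would add less than 0.01 point to Cum%Ae at an 18- or 30-day half-life (30 days: 0.0218% × 0.384 = 0.008). The window is a pragmatic choice: if a whole dose cleared at 60 to 90 days, about 0.3 to 0.9 points could still appear, which is why the second step is useful.
2. State in SAP 9.1.2 and 10.1.2 that quantifiable pre-dose TR is flagged and that the primary mass balance and parent:TR summaries are repeated without that subject. The scheduled pre-dose blood and plasma samples supply the data even when pre-dose excreta are missing. The same text should say whether pre-dose radioactivity is subtracted at any stage, including in the laboratory.

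The cost is one eligibility line, a short SAP addition, a slightly smaller volunteer pool and at most one extra sensitivity summary. No new samples are needed.
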